Aim 3: (Phase 2- HUM 00169371) Integrate personalized glaucoma education and counseling during the technician visit and test the behavioral intervention's impact on adherence to follow-up care with an ophthalmologist. We hypothesize that personalized eHealth education and motivational-interviewing-based counseling will improve adherence to glaucoma follow-up care compared to standard education delivered by a trained staff member. We will test our hypothesis in a randomized controlled trial with participants (n=400) from Aim 2 who have glaucoma or suspected glaucoma. We will make iterative refinements to our existing evidence-based, individualized counseling/eHealth glaucoma education program with a focus on adherence to follow-up recommendations based on learning in Aim 1. The primary outcome is the proportion of participants attending the recommended physician appointments within three months. Secondary outcomes include glaucoma knowledge, satisfaction with communication, and confidence in asking the ophthalmologist questions. Program economic efficiency will be assessed.

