## Planned Analysis Results Nov. 14, 2023

A planned analysis reported no difference in adherence between the intervention (personal coaching) and the control (standard education). Therefore, we will no longer randomize glaucoma/glaucoma suspect participants and instead ask them to choose which education they would like to receive.

**Follow-up surveys:** All returning participants will complete a satisfaction survey. The intervention group will also be asked to complete; 1) National Eye Institute Glaucoma Eye-Q test, 2) Satisfaction with Information Scale, 3) Clinician and Group Survey of the Consumer Assessment of Healthcare Providers and Systems (CG- CAHPS), 4) Health-Care Climate- eye care (HCCQ), 5) Confidence in question asking, which will be assessed with the following question "How confident are you in your ability to know what questions to ask the ophthalmologist?" and will have responses ranging from 1-10 on a Likert scale where 1 is "not confident at all" and 10 is "extremely confident."

Follow-up Care with an Ophthalmologist: The ophthalmologists who remotely reviews the screening examination data will make recommendations follow-up care. All patients who screen positive for ophthalmic disease will be referred to the comprehensive ophthalmologist at the Hamilton Clinic, or to the Hope-Kellogg ophthalmology clinic that runs every two months on a Saturday. The comprehensive ophthalmologists will either provide definitive care or provide a referral for further sub-specialty care. If the patient has barriers to accessing sub-specialty care at the Hamilton clinic, social workers and financial counselors will be involved to help with logistical barriers. If a patient from Hamilton clinic

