## **Research design-Intervention**

Block randomization: Subjects will be randomized to one of two treatment arms (standard glaucoma education from handouts or personalized education with counseling) in a 1:1 ratio. The time of randomization is when the patient returns for their follow-up visit with the ophthalmic technician. Randomization will occur separately for the two clinics (stratification). A variable-block randomization scheme will be used to assure balanced assignment to the treatment arms throughout the study.

Leveraging eHealth to provide personalized glaucoma education and counseling: The web-based application for personalized glaucoma education has two components woven together into a single tool to support the conversation between the patient and the glaucoma

counselor: 1) an electronic health (eHealth) component and 2) a semi-structured, tailored interview guide to facilitate an MI-based conversation. The eHealth component provides individually tailored disease information and an explanation of a patient's test results. The counselor uses the web-based application on a tablet, to share engaging audio-visual content on a screen. The counselor walks a patient through their diagnosis and test results and what would happen to their vision if glaucoma goes untreated. The counselor then elicits an understanding of what motivates that patient to maintain their vision. The counselor explores what unique obstacles the patient has to engaging in follow-up care. The counselor then assesses the patient's motivation to attend the follow-up appointment. The counselor and patient create a concrete "action plan" that delineates the short-term plan of the steps patient will take to address any identified barriers to follow-up care, which can include addressing motivational factors in a subsequent phone visit if a patient is not interested in follow-up care.

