During the first day of training, counselors are taught to ask open-ended questions, or questions that cannot be answered with a "yes" or "no" response. They learn reflective listening, or para-phrasing what a person has said to ensure the person knows the counselor

is hearing and understanding what they say. They learn to use affirmations to praise actions people are taking towards improving their health and vision. They learn to use the elicit-provide-elicit technique to give information. This involves assessing people's knowledge prior to giving information, asking permission to give new information or advice, and then following up by eliciting the person's response to the new information in order to evaluate their understanding. This non-directive way of giving advice and information supports people's autonomy. During the second day of training, counselors are taught how to make complex reflections.

Complex reflections are statements that para-phrase what a person has said and adds significant meaning to help make a person think about the implications of their statement. Counselors learn how to promote change talk and develop an action plan to adhere to follow-up care recommendations.

Role playing is used to develop these skills using a video collection of glaucoma patients explaining their reasons for not engaging in their glaucoma management. The training consists of approximately 35% didactic material and 65% role-playing and interactive learning.

Primary outcome: The primary outcome will be adherence to the recommended follow-up appointment with the ophthalmologist within 6 months due to availability in scheduling these appointments. Six-month adherence will be used as the endpoint for all participants. Adherence in each treatment group will be calculated as the proportion of patients who attended the initial scheduled follow-up visit with an ophthalmologist as recommended after being diagnosed with glaucoma or glaucoma suspect on screening exam, dividing by the total number of patients diagnosed with glaucoma or glaucoma suspect during the screening exam and scheduled for follow-up with an ophthalmologist. This objective outcome variable will be assessed through record review by the study coordinator who is masked to the treatment allocation.

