# **Data Analysis**

Primary outcome: The primary outcome (attendance to follow-up appointment with a glaucoma specialist within three months) will be summarized with frequencies and percentages by intervention and control groups, overall and stratified by site.

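### The November 2023 analysis is worded as no difference and ends randomisation, but at the planned size a non-significant result supports only no difference detected, and six-month follow-up may not have been complete

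*Protocol*

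**What the plan says.** Under the heading "Planned Analysis Results Nov. 14, 2023", the protocol states: "A planned analysis reported no difference in adherence between the intervention (personal coaching) and the control (standard education"). The next sentence draws the consequence: "Therefore, we will no longer randomize glaucoma/glaucoma suspect participants and instead ask them to choose which education they would like to receive". Nothing else is reported there: no effect estimate, confidence interval, number randomised or analysed, or data cut-off.

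Three other places bear on how to read this note.

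- **Size.** Specific Aim 3 says: "We will test our hypothesis in a randomized controlled trial with participants (n=400) from Aim 2 who have glaucoma or suspected glaucoma". Allocation is 1:1, and by the block randomization paragraph "Randomization will occur separately for the two clinics (stratification").
- **Endpoint.** The Aim 3 primary outcome paragraph says: "Six-month adherence will be used as the endpoint for all participants". Specific Aim 3 and the Aim 3 Data Analysis section still name a three-month window.
- **Analysis.** The Aim 3 Data Analysis section says the primary outcome "will be summarized with frequencies and percentages by intervention and control groups, overall and stratified by site".

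**The concern.** The comparison of adherence between coaching and standard education is the primary question of Aim 3. The note answers it in two words and acts on the answer. Two things make that answer look stronger than the design allows.

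First, failing to detect a difference does not show that there is none. Whether a null result is informative depends on the width of its confidence interval, and the note gives none.

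Second, ending randomisation because of the analysis implies that randomisation was open until about then. With a six-month endpoint for every participant, people randomised shortly before the analysis could not all have had a full observation window. The November look would then not be the complete six-month comparison of everyone randomised.

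If the wording is carried into the trial's conclusions, readers will take coaching to have been shown to add nothing. The data may in fact be compatible with a gain of several percentage points.

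**Working it through.** **Inputs from the protocol.** Planned size 400, allocation 1:1 (200 per arm); analysis dated 14 November 2023; endpoint six months for all participants; randomisation at the technician follow-up visit, scheduled 4-8 weeks after screening; screening planned over 4 years.

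**Assumptions.** The protocol shown gives no alpha, power, control adherence or target difference for Aim 3. I take two-sided 5%, control adherence of 30-70%, and uniform accrual over 2.5-4 years up to the analysis date. I read the reported finding as a non-significant comparison. Without Aim 3 inputs the figure of 400 cannot be reproduced. They may be in the SAP, so their absence is not criticised here.

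**Step 1: precision at the planned size.** For an observed difference of zero with common adherence p, the 95% half-width is 1.96 × √(2p(1−p)/200).

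- p = 0.30 or 0.70: 1.96 × √(0.42/200) = 9.0 points
- p = 0.40 or 0.60: 1.96 × √(0.48/200) = 9.6 points
- p = 0.50: 1.96 × √(0.50/200) = 9.8 points

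A zero estimate thus leaves gains up to about 9-10 points inside the interval and excludes larger ones. If the estimate favoured coaching, larger gains would stay inside. For illustration, an estimate of 5 points near p = 0.50 gives an upper limit of about 5 + 9.8 = 14.8 points.

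**Step 2: power at 200 per arm.** Power = Φ[(d − 1.96√(2p̄(1−p̄)/200)) / √((p₁(1−p₁) + p₂(1−p₂))/200)], where d is the true gain and p̄ the mean of the two rates. For 50% versus 60%: (0.10 − 1.96 × 0.04975)/0.04950 = 0.050, so power is 52%.

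| Control adherence | Power, 10 points | Power, 15 points | Detectable gain at 80% power |
|---|---|---|---|
| 30% | 56% | 88% | 13.5 points |
| 40% | 52% | 85% | 13.9 points |
| 50% | 52% | 86% | 13.8 points |
| 60% | 56% | 90% | 13.2 points |
| 70% | 64% | 95% | 11.9 points |

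A true 10-point gain would be missed in roughly 36-48% of such trials. A gain of 15 points or more would probably have been found.

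**Step 3: maturity of the endpoint.** Counting from randomisation, anyone randomised after about 14 May 2023 had less than six months of observation on 14 November 2023. Under uniform accrual the share affected is the window divided by the accrual time.

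- 4 years: 0.5/4 = 12.5%, or 50 of 400
- 2.5 years: 0.5/2.5 = 20%, or 80 of 400

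With the three-month window the shares halve, to about 6-10% (25-40 of 400). If only the 320-350 participants with a complete six-month window were analysed, the half-width for a zero estimate is 9.6-11.0 points. Power for 10 points from 40-60% is then 44-50%.

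**The case against.** The strongest reply is that the note is a short procedural statement about future participants. It does not call itself final, claim equivalence, or cancel follow-up of those already randomised. The analysis is described as planned, so a stopping rule, a target difference and an analysis set limited to complete windows may all be in the SAP, which is not shown. That is a fair limit, and no missing stopping rule is alleged.

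A reader might infer that participants with unfinished follow-up were counted in the November analysis. The protocol does not support this. It gives no data cut-off, analysis set or date of last randomisation, and restricting the analysis to complete windows would be ordinary practice. Nor does it say when the six-month clock starts. Counted from screening, with randomisation 4-8 weeks later, people randomised up to about 11 June to 9 July 2023 would have been complete. Some outcomes may also be known before six months, because the outcome is attendance at the initial scheduled visit.

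A reader might also infer that 400 participants cannot exclude a useful effect. That goes too far. 400 is the planned number, the number analysed is not given, and the protocol names no useful gain. A zero estimate at 400 would exclude gains above about 10 points, and an estimate favouring standard education would exclude smaller ones.

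What the reply does not remove is the wording. The null statement is the only reason given for ending randomisation, and it comes with nothing that would let a reader judge what it rules out.

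**Conclusion.** The point holds in limited form and should be corrected. At the planned size, a non-significant comparison supports saying that no difference was detected. It does not support saying that there is none: a zero estimate leaves gains up to about 9-10 points open, and power for a 10-point gain is only about 52-64%. These figures rest on 200 per arm, two-sided 5% and adherence of 30-70%; only the first follows from the protocol.

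Incomplete follow-up is a conditional concern. If randomisation continued to about the analysis date, roughly 12.5-20% of 400 had not completed six months, given uniform accrual over 2.5-4 years and a clock starting at randomisation. In that case the November look could not be the complete six-month comparison of everyone randomised. How those participants were handled is unknown, so no error is established.

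**What to change.** 1. Reword the note to say that no difference was detected. Give the data cut-off, the number randomised and analysed per arm, and the estimate with its interval.
2. Label the November 2023 result interim, unless it already covered every randomised participant with a complete six-month window. If it did, stating so settles the timing question.
3. Define the Aim 3 primary result as one analysis of all participants randomised before the switch to participant choice, run once the last six-month window has closed. Exclude those who chose their education. State when the six-month clock starts.
4. Report a risk difference stratified by clinic (for example Mantel-Haenszel) with a 95% CI, in keeping with the stratified randomisation and alongside the planned summaries by site.
5. Have the team name the smallest gain that would matter. Describe the result as inconclusive unless the interval excludes that gain.

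The cost is a change of text and one re-run on records already collected, with no new participants. The downside is that the headline may become inconclusive.

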Glaucoma or glaucoma suspect: Patients with a diagnosis of glaucoma or glaucoma suspect who speak English will be randomized (1:1) to receive standard care as described above, or a 60-minute personalized counseling and education program (intervention) about their diagnosis and the importance of glaucoma follow-up care in maintaining vision (Aim 3)). Ocular hypertension that is low risk for developing glaucoma within one year and/or the recommended follow up time period is one year or more, will not be randomized, the PI will review these cases to determine if they should be randomized or not. Randomization will occur in web-based randomization system. Both groups will be provided support scheduling their ophthalmologist exam and will be asked to complete a brief satisfaction survey. The standard care group will receive a reminder call prior to the ophthalmologist exam, while the intervention will receive a

reminder call as well as a 10-15 minute motivational-interviewing based- counseling follow-up phone call to remind them of why following up for glaucoma care is important to them and trouble-shoot barriers to attending. Further discussion regarding personalized counseling and motivational interviewing can be found later in this protocol. All non-English speaking patients will not be randomized and will receive standard of care education; the personalized counseling is only available in English. We have created a Spanish version of the personalized counseling. Spanish speaking participants will not be randomized, all will receive the personalized coaching session. A Spanish speaking study coordinator will conduct the Spanish eHealth coaching. All subjects participating in the counseling/education encounters will have the option to have their sessions be audio-recorded. Additionally, we will ask English and Spanish speaking participants to complete a visual field test at this appointment. A visual field test measures peripheral vision and is used to review glaucoma patients. This test will take about 20 minutes and there will be no charge to the participant or their insurance. Visual field data will be entered into the REDCap database.

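### Glaucoma knowledge and question-asking confidence are secondary outcomes of the randomised trial, but their instruments are assigned to the intervention group only

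*Protocol*

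**What the plan says.** Under Specific Aim/Hypothesis, Aim 3 sets up the comparison: "We will test our hypothesis in a randomized controlled trial with participants (n=400) from Aim 2 who have glaucoma or suspected glaucoma". The comparator is standard education. The same paragraph continues: "Secondary outcomes include glaucoma knowledge, satisfaction with communication, and confidence in asking the ophthalmologist questions".

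The survey schedule for the follow-up visit is in the Follow-up surveys paragraph, which sits under the heading Planned Analysis Results Nov. 14, 2023. It begins with everyone: "All returning participants will complete a satisfaction survey". It then adds: "The intervention group will also be asked to complete; 1) National Eye Institute Glaucoma Eye-Q test". The list goes on to the Satisfaction with Information Scale, CG-CAHPS, HCCQ and a single question-asking confidence item scored 1 to 10.

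The Glaucoma or glaucoma suspect paragraph states what both arms receive: "Both groups will be provided support scheduling their ophthalmologist exam and will be asked to complete a brief satisfaction survey". It also describes coached participants outside the randomisation: "Spanish speaking participants will not be randomized, all will receive the personalized coaching session". After the November 2023 analysis the protocol says: "Therefore, we will no longer randomize glaucoma/glaucoma suspect participants and instead ask them to choose which education they would like to receive".

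**The concern.** A secondary outcome of a randomised trial needs to be measured in both arms, in the same way and at the same time. Here the evident measure of knowledge (the Eye-Q) and the only measure of question-asking confidence are assigned to one arm. The three other named scales, any of which might have served for satisfaction with communication, are assigned to that arm too. A mean score among coached participants has no comparator and cannot be read as an effect of the counselling.

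The risk of misreading is real because the planned analysis found no difference in adherence. Readers may then look to the secondary outcomes for signs of benefit, and a one-arm score labelled as a trial outcome could be taken for one.

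A smaller point concerns who is counted. Coaching was also given to Spanish speakers who were never randomised and, after November 2023, to people who chose it. The survey paragraph does not say whether these people belong to the intervention group for survey purposes. If they do, the score mixes randomised, never-randomised and self-selected participants.

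**Working it through.** The protocol states no power, effect size or standard deviation for these outcomes, so there is no figure of its own to reproduce. The check is whether any section gives controls the five instruments.

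**Step 1. What each survey section assigns**

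| Protocol section | Who completes it | Any of the five instruments? |
|---|---|---|
| Baseline Surveys | All screened participants | No. VFQ-9, Flint water, discrimination, stress, loneliness, falls, Timed Up & Go, socio-demographics and health history |
| Follow-up (including the phone call to people with no disease and no need for glasses) | All, by visit or phone | No. Satisfaction survey only |
| Glaucoma or glaucoma suspect | Both trial arms | No. Brief satisfaction survey only |
| Follow-up surveys | All returning participants | No. Satisfaction survey only |
| Follow-up surveys | Intervention group | Yes, all five |
| One-Year Vision Outcomes | Returning participants | No. Limited to demographics, VFQ-9 and falls |
| Two-Year Vision Outcomes | Returning participants | No. Repeats the initial visit protocol; VFQ-9 by phone for those who do not return |

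**Step 2. Count**

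- Instruments assigned to controls: 0 of 5.
- Secondary outcomes with no control data as written: 2 of 3 (knowledge, confidence).
- Third outcome (satisfaction with communication): undetermined. Controls complete a satisfaction survey, but its content is not given. It is also administered by phone to people with no eye disease, which suggests a general programme survey. The protocol does not say which instrument measures this outcome.
- None of the five is listed at baseline, so a before-after change within the coached arm is not available either.

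**Step 3. Does the intervention group exclude controls?** Yes. The paragraph directly above the survey list equates the intervention with personal coaching and the control with standard education. The Glaucoma or glaucoma suspect paragraph likewise sets the intervention against the standard care group.

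**Step 4. What is lost, for illustration only.** The planned 400 at 1:1 give 400/2 = 200 per arm. As written, up to 200 coached and 0 control participants would have Eye-Q or confidence scores. Had both arms been surveyed, the detectable standardised difference at two-sided 5% and 80% power would be

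(1.960 + 0.842) × √(2/n per arm)

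- n = 200: 2.802 × √(2/200) = 0.28 SD
- n = 150: 2.802 × √(2/150) = 0.32 SD
- n = 100: 2.802 × √(2/100) = 0.40 SD

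The alpha, power, complete response and arm sizes are assumptions; the protocol does not state how many had been randomised when randomisation stopped. With no control responses there is no contrast at any n.

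**The case against.** The best counter-argument is that this may be loose drafting. The survey paragraph contrasts everyone who returns, for glasses or any eye disease, with a narrower group, and its author may have meant all Aim 3 participants. Controls may in fact have been surveyed. The document cannot rule that out, so the conclusion holds only for the plan as written. As a reading of the text it is weak. The protocol uses intervention and control as opposites in the same place, and it says plainly when it means both groups.

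Four narrower objections have some force.

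- The term intervention group is clear enough to exclude controls. What is unclear is only whether it takes in coached participants who were not randomised. No section plans a pooled score, so pooling is a possibility and not a stated intention.
- The protocol does not link the Satisfaction with Information Scale, CG-CAHPS or HCCQ to satisfaction with communication. The firm claim is therefore limited to knowledge and confidence.
- The detectable differences do not measure the defect. They show only what a two-arm comparison could offer.
- The stated hypothesis of Aim 3 concerns adherence alone, which limits how serious the point can be.

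Leaving the matter to a statistical analysis plan does not answer the concern. Such a plan governs the analysis of collected data and cannot create control responses.

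**Conclusion.** The concern holds. The outcome list in Aim 3 and the Follow-up surveys paragraph contradict each other. Followed as written, the trial has no between-arm estimate for at least two of its three named secondary outcomes, whatever the number randomised. The third cannot be judged from the protocol.

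This rests on the text alone and on one ordinary inference: that the Eye-Q is the measure of glaucoma knowledge. Whether controls were surveyed in practice is unknown. The adherence comparison is not touched. The point should be fixed because it affects what may be claimed from named trial outcomes, but it does not threaten the main result.

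**What to change.** Check the study database for which randomised participants completed the five instruments, then reconcile the two sections.

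1. **If randomised controls completed them:** correct the Follow-up surveys paragraph to say that both randomised arms do so, at the same time point. Map each secondary outcome to one instrument, including the one for satisfaction with communication. Compare by randomised arm among those randomised before the November 2023 change.
2. **If they did not:** restate the affected outcomes in Aim 3 as descriptive measures of the intervention arm, not as tests of the intervention.

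In either case:

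- State whether the intervention group in the survey paragraph means only those randomised to coaching.
- Report randomised participants separately from Spanish-speaking and self-selected coached participants. The Aim 3 strategy text lets Spanish speakers choose their education from March 2024, so they are not one uniform group.
- Label any collection in both groups after randomisation ended as a non-randomised, self-selected comparison.
- Date the amendment and give its reason, because the adherence result was already known.

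The cost is a database check and a wording change, with no new visit or data collection. If controls were not surveyed, the edit makes the record accurate but does not recover the randomised contrast.
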